# Serum chloride concentrations

Low serum chloride is associated with adverse outcome in patients with HF. We estimate a clinically meaningful change in chloride to be -0.9 mmol/L per day over the course of an admission (9 days) and -3.6 mmol/L over the four day period of our study (appendix 7). To detect such a difference with 80% power and 5% two-tailed significant with the above anticipated drop out rate we would need to recruit a minimum of 14 patients in the control arm and 17 patients in the ACZ arm.

We expect two potential confounding factors for the co-primary endpoints: 1) daily salt intake and 2) loss of IV access reducing the amount of IV furosemide given. We will collect data on both potential confounders using a daily dietary sheet (on which the patient will record their meals for the day and from which the daily salt intake will be estimated) and recording the "number of hours of furosemide" per day. We do not expect any patient to have excessive salt intake (defined by the European Society of Cardiology Heart Failure Guidelines 2021 as >5g per day). Any patient with >5g salt intake per day or <20 hours of furosemide per day will be removed from the analysis. Due to the exploratory nature of the study we will conduct an intention to treat analysis and a per-protocol analysis in which only patients who completed the study without deviating from the protocol will be included. Thus, we will recruit a maximum of 50 patients – 23 in the control arm and 27 in the ACZ arm with anticipated drop out of 10% and 20% respectively. The extra patients recruited will also act as a contingency should any patient need to be removed from the analyses for reasons of excess salt intake, prolonged loss of IV access, or for the per-protocol analysis.

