# 3.4 **Primary endpoint/outcome**

Difference in mean net fluid loss daily and over a 4 day period

• Total volume intake in millilitres (mL) – total volume passed as urine in mL

Difference in serum chloride concentrations between day 1 and day 4

• Serum chloride day 4 – serum chloride day 1

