# Visit 5 - Day 4 – 72 hours

- Furosemide infusion to continue if clinically indicated
  - If patient deemed to not require standard of care by day 4 and has their diuretic treatment de-escalated the patient will be deemed to have completed the study and further study-related investigations not carried out.
  - Body weight, blood pressure and heart rate measured by nursing staff
- Bloods taken

.

- o Urea and electrolytes
- o Full blood count
- Acetazolamide 250mg to be given by ward staff in the morning (72 hours after first dose) and 6 hours later (in ACZ group only) as per electronic prescription
- Ongoing input from treating team: ward round and any input that stems from that, regular observations from nursing staff, input from other health professionals if indicated (for example dieticians, physiotherapists, occupational therapists)
- Study doctor visit (72 hours +/- 2 hours from first dose of ACZ (ACZ arm) or randomisation (SoC arm)
  - o Clinical examination and medical history
  - Diet sheet collected from previous day
  - o Fluid balance and urine output
  - o 24 hour urine collection to begin 72 hours from first dose of ACZ or randomisation
    - Patient asked to empty bladder or nursing staff to empty catheter bag and then begin urine collection
  - Patient assessed breathlessness using 5-point Likert breathlessness scale

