# Serum Chloride Change

Data on clinically significant changes in serum chloride levels are lacking. Furthermore, there is conflicting data on the prognostic significance of reductions in serum chloride during in-patient diuresis. However, low serum chloride (<96 mmol/L – hypochloraemia) is strongly and independently associated with adverse outcome in both in- and out-patients with HF. In the PROTECT study patients with hypochloraemia on admission which had corrected by the time of discharge (day

14) were at no greater risk of mortality after discharge than those who had never had hypochloraemia. The median change in chloride between day 1 and day 14 for patients in that group was 5.5 mmol/L (interquartile range (IQR) 4 – 9mmol) which equates to a difference of 0.4 (0.3 - 0.6) mmol/L per day. Conversely, those with normal chloride levels on admission who had developed hypochloraemia by day 14 had a three-fold greater risk of mortality compared to those with normal chloride levels at day 1 and day 14. The median change in chloride between day 1 and 14 for this group was -7 mmol/L (95% CI -10 – 5) equating to -0.5 (-0.7 – 0.4) mmol/L per day.

Data from our local population found similar results: those with hypochloraemia on admission who had normal chloride by the time of discharge were at no greater risk of mortality compared to those who had normal chloride levels on admission and discharge. The median change in chloride levels in this group was 6 (5 – 8) mmol/L over a median in-patient stay of 12 days; 0.5 (0.4 – 0.7) mmol/L per day. Conversely, those with normal chloride levels on admission who had hypochloraemia at discharge were at 50% increased risk of adverse outcome. The median change in chloride levels in this group was -8 (-12 – -5) mmol/L over a median in-patient stay of 13 days; -0.6 (-0.9 – -0.4) mmol/L per day. The median chloride on admission in patients with normal chloride levels on admission was 100 (98 – 103) with a standard deviation of 3 mmol/L thus a 8 mmol/L reduction in serum chloride concentrations would cause hypochloraemia in the majority of patients; similar to the median change in chloride levels on admission who develop hypochloraemia by discharge (table 2).

Table 2 – Available Data on Changes in Serum Chloride Levels During In-patient Diuresis

Study		Ter Maarten et al	[name] et al
		(2016)	(2022)

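### The chloride sample size assumes a four-day difference of 3.6 mmol/L, but the endpoint spans 72 hours; the plan's own daily rate then gives 2.7 mmol/L and about 60% power at the stated size

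*Protocol*

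**What the plan says.** Section 10.1 (Serum chloride concentrations) takes 0.9 mmol/L per day over a 9-day admission as clinically meaningful and converts it to "3.6 mmol/L over the four day period of our study". The size is set "To detect such a difference with 80% power and 5% two-tailed significant with the above anticipated drop out rate" (10% control, 20% acetazolamide), giving 14 + 17 = 31. Planned recruitment is 40, with a maximum of 50 (23 + 27). Section 10.1 gives no SD and cites an appendix 7; the supporting data are in Appendix 2.

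Section 3.4 defines the endpoint as "Serum chloride day 4 – serum chloride day 1". Section 7.8 labels the visit "Visit 5 - Day 4 – 72 hours". The schedule in Section 7.7 lists urea and electrolytes at 0, 24, 48 and 72 hours. Visit 6 (96 hours) lists fluid balance, urine output and the end of a urine collection, but no bloods.

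Appendix 2 reports, for local patients who became hypochloraemic, a median change of -8 (-12 to -5) "mmol/L over a median in-patient stay of 13 days; -0.6 (-0.9 – -0.4) mmol/L per day". The PROTECT figure for the same kind of patient is -0.5 per day. The groups whose hypochloraemia corrected changed by 0.4 to 0.5 per day. The only chloride SD is the "standard deviation of 3 mmol/L" given for admission values.

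**The concern.** The sample size multiplies a daily rate by four, while the endpoint accrues that rate for three days. The two co-primary endpoints also cover different windows: fluid loss runs to 96 hours, and serum chloride stops at 72 hours, before the fourth day of treatment has acted.

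Two inputs add to this. The daily rate is higher than any median in the appendix cited for it, and the SD is of a level rather than of the change being analysed.

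Section 4 says the trial is powered for superiority on both primary endpoints, and Sections 2 and 10.1 say the results will inform a larger trial. If the power behind a null chloride result is overstated, that result could be read as stronger evidence against a chloride effect than it is.

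**Working it through.** **Inputs.** Two-sided 5%, 80% power, drop-out 10% and 20%, stated size 14 + 17 (Section 10.1). SD 3 is an assumption borrowed from admission chloride in Appendix 2. Evaluable patients are recruited × (1 - drop-out):

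- 31: 14 × 0.9 = 12.6 and 17 × 0.8 = 13.6
- 40 (1:1): 20 × 0.9 = 18 and 20 × 0.8 = 16
- 50: 23 × 0.9 = 20.7 and 27 × 0.8 = 21.6

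**Reproducing the plan.** n per arm = 2 × (1.96 + 0.84)² × (3/3.6)² ≈ 10.9, so 11. The exact t version gives 12. Inflated: 12/0.9 = 13.3, so 14 control; 12/0.8 = 15 acetazolamide. That is 29 against the stated 31. At 14 + 17 the power for 3.6 is about 84%. The stated size therefore follows closely from 3.6 and SD 3.

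**Window.** 0.9 × 4 = 3.6, but 0.9 × 3 = 2.7 over 0 to 72 hours.

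**Rate.** 8/9 = 0.89, which matches the plan's 0.9. Appendix 2 says the 8 mmol/L fall took 13 days in the text (8/13 = 0.62) and 12 in its table (8/12 = 0.67). PROTECT: 7/14 = 0.5. In Appendix 2 itself, 0.9 per day is printed only as the outer quartile of the local cohort. At 0.6 per day: 0.6 × 4 = 2.4 and 0.6 × 3 = 1.8.

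**Power.** Noncentral t with noncentrality Δ / (SD × √(1/n₁ + 1/n₂)) on n₁ + n₂ - 2 degrees of freedom. Example, 2.7 at 31 recruited: √(1/12.6 + 1/13.6) = 0.391; 2.7 / (3 × 0.391) = 2.30; critical t = 2.06; power about 60%.

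| Difference, SD 3 | 31 recruited | 40 | 50 |
|---|---|---|---|
| 3.6 (0.9 × 4) | 84% | 92% | 97% |
| 2.7 (0.9 × 3) | 60% | 72% | 81% |
| 2.4 (0.6 × 4) | 50% | 62% | 72% |
| 1.8 (0.6 × 3) | 31% | 40% | 48% |

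The difference detectable with 80% power is 0.993 × 3 = 2.98 mmol/L at 40 and 0.883 × 3 = 2.65 at 50.

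**SD.** Taking IQR/1.349 as a rough SD of change:

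- local corrected group (5 to 8): 3/1.349 = 2.2
- PROTECT corrected group (4 to 9): 5/1.349 = 3.7
- local incident group (-12 to -5): 7/1.349 = 5.2

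These are changes over 12 to 14 days in groups selected on their chloride course, so they only bracket the SD of a three-day change. For 2.7 mmol/L at 40 recruited, power is about 93% at SD 2.2, 72% at 3, 54% at 3.7 and 31% at 5.2.

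**The case against.** Power is conditional on a target, and 3.6 is put forward as a clinically meaningful change, not a forecast. Appendix 2 gives a reason for the 8 mmol/L (it would make most patients hypochloraemic), and spreading it over the 9-day UK median stay is a choice, if a thinly argued one. That stands: the rate is poorly justified, and the calculation from it is not an arithmetic slip. The appendix medians are not firm replacements either. They assume a linear change over about two weeks, and the PROTECT patients received 80 mg of diuretic a day against 240 mg here.

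It can also be said that this is a pilot, that Section 10.1 admits the calculation may look crude, and that the fluid endpoint (35) rather than chloride drives recruitment. This lowers the severity. It does not remove the mismatch, because Section 4 claims power on both endpoints.

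A reader might take day 4 to mean the end of the fourth day, since the protocol does use it loosely: Section 13.3 puts the second ultrasound on day 4, whereas the schedule has it at 96 hours. For serum chloride that reading fails, because no blood is scheduled at 96 hours.

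Three stronger readings are not supported:

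- **True power is 30 to 60%.** That range belongs to the 31-patient minimum, with SD 3 and a true difference of 1.8 to 2.7. At the planned sizes the same differences give 40 to 72% (40) and 48 to 81% (50).
- **A difference of 3.6 requires acetazolamide to abolish the whole fall in chloride.** Sections 1 and 2 anticipate that the drug may raise serum chloride, so a treated rise could add to a control fall.
- **No study electrolytes follow the last doses.** The 72 to 96 hour urine collection covers sodium, chloride and potassium; only serum is missing.

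**Conclusion.** The point holds as a mismatch between the sample size and the endpoint. The stated 80% at 31 patients applies to a four-day difference that the scheduled samples cannot measure. On the plan's own daily rate the 72-hour difference is 2.7 mmol/L, with about 60% power at 31, 72% at 40 and 81% at 50. At 0.6 per day, the highest median rate printed in Appendix 2, these become about 31%, 40% and 48%.

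All of these rest on SD 3, the stated drop-out rates and a 1:1 split at 40. The SD is the weakest input: at 2.2 even 2.7 mmol/L at 31 recruited would have about 85% power, and at 5.2 about 25%. The 81% at 50 also uses patients whom Section 10.1 sets aside partly as cover for exclusions.

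The documents support saying that the chloride power is misstated for the endpoint and thinly justified. They do not show that the trial is underpowered by any single amount. Severity: should fix.

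**What to change.** 1. Choose one window. Either keep the 72-hour endpoint and restate the target as three times the daily rate, or schedule a serum chloride at Visit 6 (96 hours) and define it as the end value in Sections 3.4, 7.7, 7.8 and 10.3, so that both co-primaries cover the same period.
2. Justify the daily rate against the Appendix 2 medians, say whether it is a target or an expected between-arm difference, and correct the reference to appendix 7. Reconcile the 12- and 13-day stays, which the text and table of Appendix 2 give the opposite way round.
3. State an SD of the change in chloride and show a range of about 2 to 5.
4. Report power, or the difference detectable with 80% power, at 40 and 50 rather than only at 31: about 3.0 and 2.65 mmol/L if the SD is 3.

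The cost is mostly wording, and the stated power becomes less favourable. The 96-hour option needs one blood result written into the schedule. It cannot be left to routine care, because Section 7.8 assures routine biochemistry only every 48 hours although the Trial Summary describes it as daily.

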# **10.2** Planned recruitment rate

There are, on average, 10 patients with heart failure on the Cardiology wards at CHH in any given week, each with a median stay of 9 days. Entry criteria are broad and exclusion criteria minimal with the intent that enrolment is as representative a population as possible. It is expected to be able to recruit at least 2 patients per week. This estimate may seem conservative however after enrolment, the patient will have daily visits from the study doctor with collection of multiple data points and the associated paper work to complete. Thus we estimate recruitment to take 20-30 weeks.

# 10.3 Statistical analysis plan

# Baseline data

# Primary outcomes

Differences in daily net fluid loss and total change in serum chloride (day 1 to day 4) will be compared using independent samples T test. If a difference in number of hours of furosemide per day or salt intake per day is different between the groups then the change in the primary outcomes will be stratified sub groups of hours of furosemide per day and grams of salt per day (cut-offs for group membership will be identified post-hoc).

# 10.3.1 Summary of baseline data and flow of patients

Baseline characteristics (Table 2) will be described as median (25th - 75th centiles) for continuous data and total number (percentage of population) for categorical data. Normality of distribution will be assessed by plotting bell-curves for each continuous variable.

Patient entry into the study will be described using a consort flow diagram.

Table 2: Baseline table

	Acetazolamide	Control	Р
	N = X	N = X	
Age – years			
Sex – male (%)			
IHD – N (%)			
Diabetes – N (%)			
Hypertension – N (%)			
COPD – N (%)			
Atrial fibrillation – N (%)			
Cancer – N (%)			
"De novo" HF – N (%)			
Ischaemic cardiomyopathy – N (%)			
DCM – N (%)			
LVEF - %			
LVEF <40% - N (%)			
Valve disease – N (%)			
Mod or worse AS – N (%)			
Mod or worse MR – N (%)			
Weight – kg			
BMI – kg/m 			
SBP – mmHg			
Heart rate – bpm			
NYHA class IV			
Likert breathlessness scale			

Peripheral oedema affecting up		
to:		
ankles – N (%)		
knees – N (%)		
sacrum – N (%)		
Lung crackles		
None – N (%)		
Bibasal – N (%)		
Mid-zone – N (%)		
Whole lung – N (%)		
Jugular venous pulse		
Not visible – N (%)		
Raised 1-4m – N (%)		
>4cm – N (%)		
Level of Earlobes – N (%)		
NTproBNP – ng/L		
Haemoglobin – g/dL		
Haematocrit – fraction		
Sodium – mmol/L		
Chloride – mmol/L		
Potassium – mmol/L		
Bicarbonate – mmol/L		
Urea – mmol/L		
Creatinine - µmol/L		
Estimated Glomerular Filtration		
Rate – ml/min/1.73m 		
Albumin – g/dL		
Inferior vena cava diameter –		
cm		
ACEI/ARB/ARNI – N (%)		
ACEI or ARB – N (%)		
ARNI – N (%)		
Beta-blocker – N (%)		
MRA – N (%)		
Median oral loop diuretic dose		
prior to admission (mg / day)		
Median intravenous loop		
diuretic dose received as an in-		
patient prior to randomisation		
(mg / day)		

# 10.3.2 Primary outcome analysis

# Primary outcomes

We will calculate the median net fluid loss each day and from baseline to day 4 for patients in the ACZ arm and the control arm. We will assess distribution of daily and total fluid loss in both arms, if there is normal distribution we will compare the median net fluid loss using independent samples T-test, if the distribution is not normal we will use the Mann-Witney-U test. A P value <0.05 will indicate a statistically significant difference between the two arms. We will also perform linear regression with total net fluid loss from day 1 to day 4 as the dependent variable and treatment assignment, median daily salt intake and median number of hours of furosemide per day as the independent variables.

We will calculate the median change in serum chloride concentrations between the two groups between baseline and day 4. We will compare the median change in serum chloride concentration using independent samples T test. We will also perform linear regression with total change in serum chloride levels day 1 to day 4 as the dependent variable and treatment assignment, median daily salt intake, and median number of hours of furosemide per day as the independent variables.

The independent samples T test assumes that both net fluid loss (daily and total) and change in serum chloride concentrations between day 1 and day 4 are normally distributed in both groups; this will be tested using distribution curves. It also assumes that there is equal variance in both net fluid loss (daily and total) and change in serum chloride concentrations between day 1 and day 4; this will be tested using Levene's test, the samples will be assumed to have equal variance if Levene's test is P>0.05.

We do not expect any missing data, however any patient with missing data for each of the co-primary endpoints will be excluded from the analysis.

We expect two potential confounding factors for the co-primary endpoints: 1) daily salt intake and 2) loss of IV access reducing the amount of IV furosemide given. Any patient with >5g salt intake per day or <20 hours of furosemide per day will be removed from the analysis.

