Whether acetazolamide has a significant diuretic effect in patients also taking standard treatment in the UK (240mg / 24 hours IV furosemide infusion) is unknown. Furthermore, how it affects renal chloride excretion and whether it can correct hypochloraemia or prevent incident hypochloraemia due to high dose loop diuretic is unknown.

There is a pressing need to clarify whether or not acetazolamide can increase diuresis and / or favourably affect renal chloride excretion. Our pilot and exploratory study will provide data to estimate the effect of acetazolamide on diuresis and serum chloride concentrations during treatment with IVI of furosemide at 10mg/hr (standard of care in the UK for patients admitted with severe venous congestion).

It will also provide data on the possible tolerability of acetazolamide and recruitment rate to a study of acetazolamide in patients hospitalised with heart failure in the UK.

Should the data suggest a favourable effect on either diuresis and / or chloride homeostasis during diuresis then the results of study will be used to design a large multi-centre randomised placebo controlled trial of acetazolamide combined with high dose loop diuretics to prevent or correct hypochloraemia during in-patient diuresis.

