# 3.2 Primary objective

# Primary hypothesis

The addition of 250mg acetazolamide orally twice-daily to 240mg / 24hr IV furosemide infusion willNHS Trust increase diuresis while also reducing the amount by which serum chloride concentrations fall during diuresis in a patient admitted to hospital for venous congestion due to heart failure compared to furosemide infusion alone.

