# 4 TRIAL DESIGN

This will be an open label, randomised, controlled pilot and exploratory study which will be powered to detect superiority of the addition of acetazolamide 250mg BD by mouth (PO) in conjunction with 240mg/24 hours furosemide IVI on diuresis and chloride homeostasis compared to 240mg/24 hours IV furosemide infusion alone (standard of care) both primary endpoints with the primary aim of gathering data on the feasibility and tolerability of the intervention which will inform a larger study.

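### Up to six comparisons carry primary status at a nominal 5% each, with no deciding fluid contrast and no rule for combining the two co-primary endpoints

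*Protocol*

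**What the plan says.** **Endpoints.** Section 3.4 lists "Difference in mean net fluid loss daily and over a 4 day period" and "Difference in serum chloride concentrations between day 1 and day 4". That is four daily fluid comparisons, one fluid total and one chloride comparison.

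**Analysis.** Section 10.3, under the primary outcomes, names only daily fluid loss beside chloride: "Differences in daily net fluid loss and total change in serum chloride (day 1 to day 4) will be compared using independent samples T test". Section 10.3.2 uses both daily and total fluid loss ("We will calculate the median net fluid loss each day and from baseline to day 4 for patients in the ACZ arm and the control") and gives the threshold in the same paragraph: "A P value <0.05 will indicate a statistically significant difference between the two arms". The chloride paragraph of 10.3.2 has no threshold of its own. Its 5% two-tailed level comes from the sample size text in 10.1. Each endpoint also gets a linear regression whose status is not given.

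**How the two endpoints combine.** The primary hypothesis in 3.2 is that the drug will "increase diuresis while also reducing the amount by which serum chloride concentrations fall during diuresis", which asks for both effects. The null hypothesis in 3.2 denies an effect on diuresis or on chloride, so an effect on one of them contradicts it. The rationale in Section 2 looks to a larger trial "Should the data suggest a favourable effect on either diuresis and / or chloride homeostasis during diuresis", where one effect is enough.

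**Status of the trial.** The study is called pilot and exploratory throughout. Section 4 also says it is "powered to detect superiority of the addition of acetazolamide 250mg BD by mouth (PO") on both primary endpoints. Section 13.10 says that finding a treatment benefit is outside what the study was designed to do. Only the secondary outcomes are declared unpowered (10.3.3).

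**The concern.** A 5% level on each of several primary comparisons keeps the overall error at 5% only if all must succeed, or if one of them is named in advance as decisive. The protocol does neither. Three readings of the primary fluid result are open: the 4-day total, a particular day, or any day. Two readings of the pair are open: both endpoints, or either.

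Two consequences follow. One significant day out of four could be reported as a positive primary result while the 4-day total shows nothing. And a mixed result, say fluid P=0.03 with chloride P=0.20, falls short of the primary hypothesis yet fits the rationale's condition for planning a large trial. In an open-label study, a contrast or rule chosen after the results are seen cannot be repaired.

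**Working it through.** **1. The protocol's own sample size.** Inputs from 10.1: difference 500–1000 mL/day, SD 500–1000 mL/day (ratio 1 if the ranges are paired), two-sided 5%, power 80%, drop-out 10% (control) and 20% (acetazolamide).
- n per arm = 2(1.96+0.8416)²/1² = 15.7.
- 15.7×1.1 = 17.3 and 15.7×1.2 = 18.8, truncated to the stated 17 and 18.
- Chloride: difference 3.6 mmol/L and SD 3 mmol/L give a ratio of 1.2. The SD is that of admission values in Appendix 2, assumed to be the one used. A t-test needs 12 per arm, or 14+15 after division by 0.9 and 0.8, against the stated 14+17.

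So each endpoint was sized separately at a full 5%.

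**2. Error rate if any one result counts.** Two independent tests: 1−0.95² = 9.75%. The six tests are not independent because the total is the sum of the days, so they were simulated: no treatment effect, 20 per arm, normal data, equally correlated days, two-sided t-tests at 0.05, 60,000 trials per setting, and fluid–chloride correlation 0 to 0.5.

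| Day-to-day correlation | Total or chloride | Any of six | Both total and chloride |
|---|---|---|---|
| 0 | about 10% | 24% | 0.2–0.3% |
| 0.5 | 9–10% | 19–20% | 0.3–0.9% |
| 0.75 | 9–10% | 16–17% | 0.2–0.9% |
| 0.95 | 9–10% | 12–13% | 0.2–0.9% |

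The protocol states no correlation. Appendix 2, Table 1 gives a rough guide from the ATHENA-HF interquartile ranges, assuming normality and equal daily variances (SD = IQR/1.349):
- 24 h: (1955−510)/1.349 = 1071. 72 h: (5565−2011)/1.349 = 2635. 96 h: (8132−2924)/1.349 = 3861.
- Variance of a sum of k days = k·s²·[1+(k−1)ρ], so ρ = [(SDₖ/SD₁)²−k]/[k(k−1)].
- 72 h: (6.05−3)/6 = 0.51. 96 h: (12.99−4)/12 = 0.75.
- The 48 h range gives 1.13, which is impossible, so this is a guide and not an estimate.

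Counting only false positives that favour acetazolamide, at correlations 0.5–0.75: about 4.5–5% for the two tests and 8–10% for all six, against 2.5% for a single two-sided 5% test. With no drug effect, at least one day is significant while the total is not in about 7–11% of trials.

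**3. If both must succeed.** Error is under 1% when neither effect exists, and at most 5% when only one is absent. Power comes from the noncentral t, with noncentrality (difference/SD)×√[n₁n₂/(n₁+n₂)], 1:1 allocation (7.3.1), the protocol's drop-out, and endpoints taken as independent.
- 40 randomised: 18 v 16 evaluable; fluid 80.6%, chloride 92.3%; joint 0.806×0.923 = 74%.
- 50 randomised: 22.5 v 20 evaluable; fluid 88.8%, chloride 96.8%; joint 0.888×0.968 = 86%.

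**4. If either suffices, with Holm.** The smaller P value is tested at 0.025. Fluid power there (difference = 1 SD) is about 71% with 40 randomised and 82% with 50.

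**The case against.** The strongest reply is that this is a pilot. Section 4 makes feasibility and tolerability data the primary aim, 10.1 says the power calculation serves to inform future work and the recruitment timeline, and 13.10 disclaims detection of benefit. All of that stands, and it lowers the stakes. It does not remove the point, because Section 4 claims power for superiority on both primaries, 10.3.2 sets a significance threshold, and only the secondaries are declared unpowered.

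A second reply is that allocation of alpha is often left to a separate analysis plan, which may exist unseen. That is fair for the adjustment method. It does not cover the disagreement between 10.3 and 10.3.2 on the fluid contrast, or between Sections 4 and 13.10 on purpose, which are in the protocol itself.

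Three stronger readings are tempting and not supported:
- *That the protocol states two contradictory success rules.* It states none. The rationale sentence has no P value or test, and the hypothesis and null are not decision rules. The fault is that no rule is fixed and the wording points both ways.
- *That an inert drug would be declared effective in up to 20% of trials.* That rate is two-sided and counts every single day as a win, which no section says. In the favourable direction it is about half.
- *That requiring both endpoints leaves joint power in the sixties.* That takes exactly 80% for each. On the protocol's inputs chloride has more, and joint power exceeds 80% at the maximum of 50.

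**Conclusion.** The point holds as one of ambiguity with a measurable cost. Six comparisons have primary status, no fluid contrast decides, and nothing says how fluid and chloride combine. The inflation arises only if any one result counts: about 9–10% for the total and chloride, and 16–20% for all six, two-sided. If both are required, there is no inflation, but joint power is about 74% at the planned 40 and is not stated.

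The two-test rate hardly depends on assumptions. The six-test rate depends on the day-to-day correlation, ranging from 24% at 0 to 12–13% at 0.95. The power figures rest on a fluid difference of 1 SD, a chloride SD of 3 mmol/L and independent endpoints. If a 500 mL difference met an SD of 1000 mL, power would be far lower. It should be fixed before analysis, but it does not invalidate a 40–50 patient pilot.

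**What to change.** - In 3.4, 10.3 and 10.3.2, name two primary contrasts only: 4-day total net fluid loss, and change in serum chloride from day 1 to day 4.
- Move daily net fluid loss to the exploratory outcomes, reported as estimates with 95% confidence intervals. Label the linear regressions as supportive.
- State one decision rule and bring Section 2, both hypotheses in 3.2, and Section 4 into line with it. If an effect on either endpoint suffices, apply Holm (smaller P value against 0.025, then the larger against 0.05). If both are required, keep 0.05 for each and state the joint power.
- Reconcile Section 4 with 13.10. If the trial is meant to be purely exploratory, drop the significance and superiority wording for the primaries and report estimates with confidence intervals.

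The cost is protocol wording; no extra patients or data are needed. The downside is a lower stated power. Under Holm's first step, fluid power falls from about 81% to 71% with 40 randomised and from about 89% to 82% with 50, when the difference equals 1 SD. Under the rule that both must succeed, the figures to state are the 74% and 86% above.
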